### **1.3.2 Secondary Objectives**

[figure not shown]
- To assess the preliminary anti-tumor activity of BMS-986148 as monotherapy and in combination with nivolumab as measured by objective response rate (ORR), response duration, and progression-free survival (PFS)
- To characterize the PK of the total antibody (unconjugated antibody + antibody conjugated to tubulysin or antibody conjugated to any tubulysin metabolites), active ADC (antibody conjugated to tubulysin), and unconjugated tubulysin when BMS-986148 is administered as monotherapy and in combination with nivolumab
- To characterize the PK of nivolumab when administered in combination with BMS-986148
- To assess the effect of BMS-986148 monotherapy dosage regimen and exposure (active ADC and unconjugated tubulysin) on the QT interval
- To characterize the immunogenicity of BMS-986148 as monotherapy and in combination with nivolumab
- To characterize the immunogenicity of nivolumab in combination with BMS-986148

[figure not shown]

[figure not shown]

[figure not shown]

[figure not shown]

[figure not shown]

[figure not shown]

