#### 5) Age and Reproductive Status

- a) Males and females, 18 years of age or greater or local age of majority.
- b) Women of childbearing potential (WOCBP) must have a negative serum or urine pregnancy test (minimum sensitivity 25 IU/L or equivalent units of human chorionic gonadotrophin) within 24 hours prior to the start of study drug.
- c) Women must not be breastfeeding. WOCBP must agree to follow instructions for method(s) of contraception for the duration of treatment with BMS-986148 monotherapy plus 5 half-lives of the total antibody (approximately 60 days) plus 30 days (duration of ovulatory cycle) for a total of 90 days post-treatment completion (Part 1 and Part 2).

WOCBP must agree to follow instructions for method(s) of contraception for the duration of treatment with BMS-986148 and nivolumab combination therapy for 23 weeks (30 days plus the time required for nivolumab to undergo 5 half-lives) after the last dose of study drug (Part 3).

- d) Males who are sexually active with WOCBP must agree to follow instructions for method(s) of contraception for the duration of treatment with BMS-986148 monotherapy plus 5 half-lives of the total antibody (approximately 60 days) plus 90 days (duration of sperm turnover) for a total of 150 days post-treatment completion (Part 1 and Part 2). If treated with BMS-986148 and nivolumab combination, males who are sexually active with WOCBP must continue contraception for 31 weeks (90 days plus the time required for nivolumab to undergo 5 half-lives) after the last dose of study drug (Part 3).
- e) Azoospermic males and WOCBP who are continuously not heterosexually active are exempt from contraceptive requirements. However, the latter must still undergo pregnancy testing as described in this section.

Investigators shall counsel WOCBP and male subjects who are sexually active with WOCBP on the importance of pregnancy prevention and the implications of an unexpected pregnancy. Investigators shall advise WOCBP and male subjects who are sexually active with WOCBP on the use of highly effective methods of contraception. Highly effective methods of contraception have a failure rate of < 1% when used consistently and correctly.

At a minimum, subjects must agree to use 1 highly effective method listed below:

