PE		X	X						If the screening PE is performed within 24 hours prior to dosing on Day 1, then a single exam may count as both the screening and pre-dose evaluation. A neurological exam must be included at screening or pre-dose at the C1D1 visit.
Targeted PE						X	X	X	To include signs and symptoms of peripheral neuropathy and ocular toxicity. Any grade ocular toxicity requires ophthalmologist consultation and discussion with medical monitor as appropriate.
Ophthalmological Examination c		X							Performed by ophthalmologist or locally qualified personnel. Any abnormality must be discussed with the medical monitor prior to dosing.
Physical Measurements		X	X						Height (screening only), weight.
Vital Signs d		X	X			X	X	X	Body temperature, blood pressure and heart rate. Blood pressure and heart rate should be measured after the subject has been resting quietly for at least 5 minutes.

**Table 5.1-4: Screening and Cycle 1, Part 1B (Weekly Dosing BMS-986148 Monotherapy Dosing / 28 Day Cycle) Procedural Outline (CA008002)**

Procedure a	Pre-Screening	Screening Visit D-28 to D-1	C1D1	C1D2	C1D4 b	C1D8	C1D15	C1D22	Notes
ECGs		X	X	X		X	X		ECGs should be recorded after the subject has been supine for at least 5 minutes. Triplicate ECGs should be taken within 5 minutes of the previous measurement.  For ALL subjects in Part 1 and up to 20 subjects in Part 2: time matched for PK; triplicate evaluations at C1D1 pre-dose and EOI, C1D2 (24 hours post dose), and C1D8 (168 hours post dose) AND at C4D1 pre-dose and EOI, C4D2 (24 hours post dose), and C4D8 (168 hours post dose).  QTcF assessment > 450msec must be confirmed on repeat ECG.
MUGA/Echocardiogram		X							MUGA or echocardiogram done at screening to document LVEF. Echocardiogram done at the start of Cycle 3, then every 3 cycles thereafter, and as clinically indicated for the evaluation of pericardial effusion.
Laboratory Tests		X	X	X	X	X	X	X	If the screening laboratory is performed within 24 hours prior to dosing on Day 1, then a single exam may count as both the screening and pre-dose evaluation.  See Section 5.3.1 , Urine - screening only, unless clinically indicated.  C1D4 and C4D4: CBC only.

**Table 5.1-4: Screening and Cycle 1, Part 1B (Weekly Dosing BMS-986148 Monotherapy Dosing / 28 Day Cycle) Procedural Outline (CA008002)**

Procedure a	Pre-Screening	Screening Visit D-28 to D-1	C1D1	C1D2	C1D4 b	C1D8	C1D15	C1D22	Notes

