Clinical Drug Supplies									
Dose Level Assignment		X							At the completion of screening procedures and eligibility determination.
BMS-986148 Administration			X			X	X		Those supplied by BMS.

a In the event multiple procedures are required at a single time point, the following is a list of procedures from highest priority to low: 1) ECG, 2) PK sampling, and 3) clinical labs.

b C1D4: ± 1 day.

c Ophthalmological examination: 8-point exam (visual acuity, pupils, extraocular motility and alignment, tonometry, visual field, external examination, slit lamp examination and fundoscopy) conducted at baseline and focused exams with visual acuity, slit lamp, and as indicated will be conducted at the end of Cycle 1 (pre-dose Cycle 2), every other cycle, EOT and as clinically indicated during the study.

d Cycle 1, Day 1: vital signs will be obtained before the BMS-986148 infusion and then every 15 minutes (± 5 minutes) until 60 minutes after completion of the infusion. During subsequent treatment visits, vital signs may be obtained every 30 minutes (± 10 minutes) until 30 minutes following completion of the last infusion. If any vital sign is abnormal at the final check, the subject must be observed further for a period of time, as clinically indicated. The start and stop time of the study drug infusion should be documented (start of drug infusion = 0 hour).

█ C: cycle; CBC: complete blood cell (count); CRF: case report form; D: day; █  
█ ECG: electrocardiogram; ECOG: Eastern Cooperative Oncology Group; EOI: end of infusion; EOT: end of treatment; IHC: immunohistochemistry; LVEF: left ventricular ejection fraction; MUGA: multigated acquisition; PE: physical examination; PK: pharmacokinetics; QTcF: QT interval corrected by Fridericia's formula; SAE: serious adverse event.

**Table 5.1-5: Cycle 2 to Off Study Visit, Part 1B (Weekly Dosing BMS-986148 Monotherapy Dosing / 28 Day Cycle) Procedural Outline (CA008002)**

Procedure a	C2 and C3				C4				C5 and Beyond			EOT	Follow-up (30 and 60 Days After Last Dose)	Survival Follow- up b	Notes	
	D1	D8	D15	D22	D1	D2	D4 c	D8	D15	D1	D8	D15		(±5 days)		(±2 weeks)
Safety Assessments																
Targeted PE	X	X	X	X	X						X			X	X	To include signs and symptoms of peripheral neuropathy and ocular toxicity. Any grade ocular toxicity requires ophthalmologist consultation and discussion with medical monitor as appropriate.

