Ophthalmological Examination d	Start of Cycle 2, every 2 cycles thereafter, and as clinically indicated.												X			Performed by ophthalmologist or locally qualified personnel. Any abnormality must be discussed with the medical monitor prior to dosing. Ophthalmological exams can be done up to 72 hours prior to dosing.
Physical	X				X						X			X	X	Weight only.

**Table 5.1-5: Cycle 2 to Off Study Visit, Part 1B (Weekly Dosing BMS-986148 Monotherapy Dosing / 28 Day Cycle) Procedural Outline (CA008002)**

Procedure a	C2 and C3				C4				C5 and Beyond			EOT	Follow-up (30 and 60 Days After Last Dose)	Survival Follow- up b	Notes	
	D1	D8	D15	D22	D1	D2	D4 c	D8	D15	D1	D8	D15		(±5 days)		(±2 weeks)
Measurements																
Vital Signs e	X	X	X	X	X			X	X	X			X	X		See note in screening procedures.
ECGs	X				X	X		X	X	X			X	X		See note in screening procedures.
Echocardiogram	Start of Cycle 3, then every 3 cycles thereafter, and as clinically indicated.												X			On treatment echocardiogram exams may be done up to 72 hours prior to dosing.
Laboratory Tests	X	X	X	X	X		X	X	X	X			X	X		See note in screening procedures and Section 5.3.1 . Lab tests can be performed up to 24 hours prior to dosing. C4D4 (CBC only) collection to be time matched with PK collection pre-dose.

**Table 5.1-5: Cycle 2 to Off Study Visit, Part 1B (Weekly Dosing BMS-986148 Monotherapy Dosing / 28 Day Cycle) Procedural Outline (CA008002)**

Procedure a	C2 and C3				C4					C5 and Beyond			EOT	Follow-up (30 and 60 Days After Last Dose)	Survival Follow- up b	Notes
	D1	D8	D15	D22	D1	D2	D4 c	D8	D15	D1	D8	D15		(±5 days)	(±2 weeks)	
Tumor Biopsy (Fresh) Part 2 Only	X															C2D1 (±3 days). For 10 ovarian cancer subjects and 10 gastric cancer subjects who provided pre-treatment biopsies.
Pregnancy Test	X	X	X		X			X	X	X	X	X	X	X		
Concomitant Treatments	X	X	X	X	X	X	X	X	X	X	X	X	X	X f		
Adverse Event Reporting																
Monitor for Non-SAEs	X	X	X	X	X	X	X	X	X	X	X	X	X	X		See note in screening procedures.
Monitor for SAEs	X	X	X	X	X	X	X	X	X	X	X	X	X	X		See note in screening procedures.
PK and Immunogenicity Assessments (See Section 5.5)																
Efficacy Assessments																
Tumor Assessment	At the start of Cycle 3 and then every 2 cycles thereafter (±1 week).												X	X g	X h	See Sections 5.3.1 and 5.4.1.

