**Table 5.5.1-2: PK and ADA Sampling Schedule for BMS-986148 Monotherapy QW Dosing Regimen**

Study Day of Sample Collection	Event	Time (Relative To Start of Infusion) Hour: Min	PK Sample (Serum and Plasma)	ADA Sample (Serum)
Cycle 1				
1	Predose	00:00	X	X
1	EOI a	01:00	X	
1		04:00	X	
2		24:00	X	
4		72:00	X	
8	Predose	00:00	X	
8	EOI	01:00	X	
15	Predose	00:00	X	X
15	EOI	01:00	X	
22		168:00	X	
Cycle 3				
1	Predose	00:00	X	X
Cycle 4				

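### The weekly-regimen ECG note keeps the Q3W time points, so the ECGs already scheduled on Day 15 are not specified as triplicate or PK-matched at the expected peak of the weekly cycle.

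*Protocol*

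**What the plan says.** Protocol Section 1.3.2 sets a secondary objective: "To assess the effect of BMS-986148 monotherapy dosage regimen and exposure (active ADC and unconjugated tubulysin) on the QT interval".

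For the weekly regimen, the ECG note in Table 5.1-4 covers all Part 1 subjects and up to 20 in Part 2. It lists "time matched for PK; triplicate evaluations at C1D1 pre-dose and EOI, C1D2 (24 hours post dose), and C1D8 (168 hours post dose") in Cycle 1, and "C4D1 pre-dose and EOI, C4D2 (24 hours post dose), and C4D8 (168 hours post dose") in Cycle 4. Table 5.1-5 refers back to this note. The ECG note in Table 5.1-2, for Q3W dosing, gives the same list.

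Other parts of the weekly schedule do include Day 15:

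- **Dosing.** The row "BMS-986148 Administration X X X" in Table 5.1-4 falls on C1D1, C1D8 and C1D15.
- **ECG grid, Cycle 1.** The row "ECGs X X X X X ECGs should be recorded after the subject has been supine for at least 5 minutes" marks screening, C1D1, C1D2, C1D8 and C1D15. The Q3W grid has no Day 15 mark.
- **ECG grid, later cycles.** The row "ECGs X X X X X X X X See note in screening procedures" in Table 5.1-5 includes C4D1, C4D2, C4D8 and C4D15.
- **PK.** Table 5.5.1-2 ("PK and ADA Sampling Schedule for BMS-986148 Monotherapy QW Dosing Regimen") samples Day 15 pre-dose and at EOI in Cycles 1 and 4.

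On analysis, Protocol Section 8.4.3 tabulates changes in QTcF by dose and study day, and categories of the maximum values by dose. It says a mixed-effects concentration-QTcF model may be fitted. SAP Section 7.6.8 tabulates each subject's maximum post-dose QTcF and lists a scatterplot with regression of the QTcF change on concentration.

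**The concern.** Under Q3W dosing, the Day 1 EOI sample follows the only infusion of the cycle, so it is a sensible place for the high-concentration triplicate. Under weekly dosing, Day 1 is the first of three infusions. If the drug carries over from week to week, Day 1 EOI is the lowest of the three infusion peaks and Day 15 EOI the highest. The 168-hour Day 8 ECG is then the trough before the second dose.

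The objective names regimen as well as exposure, so QTcF data specific to the weekly schedule matter. As written, the plan never requires a PK-matched triplicate at the point of the weekly cycle where exposure is expected to be highest. A subject who leaves before Cycle 4 (Day 3 × 28 + 1 = 85) supplies listed triplicates from the first dose only. An ECG not taken alongside its PK sample cannot be paired afterwards.

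**Working it through.** **1. Was the note adapted to weekly dosing?** The two lists of time points are identical. The Day 8 label also points to the Q3W schedule. In the Q3W PK table, Day 8 is hour 168. In the weekly PK table, Day 8 is a pre-dose sample at hour 0, and hour 168 falls on Day 22. The dosing row, ECG grid and PK table were adapted; the triplicate list was not.

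**2. How far below the peak is Day 1 EOI?** The plan gives no figure to reproduce, so this is a sizing exercise under assumptions.

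Model: linear one-compartment superposition, equal doses on Days 1, 8 and 15 of each 28-day cycle, infusion treated as a bolus, no delays. Concentration is in units of the rise from one weekly dose, and h is the half-life in days.

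Half-lives used:

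- 12 d: total antibody, from "5 half-lives of the total antibody (approximately 60 days") in inclusion criterion 5, 60 / 5 = 12.
- 6 d and 3.5 d: antibody and payload of another mesothelin-directed conjugate, Protocol Section 1.5.1.
- 1 d: an assumption, to show the low end.

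None of these is a half-life for active ADC or unconjugated tubulysin, and the documents give none.

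Formulas:

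- C1D1 EOI = 1
- C1D15 EOI = 1 + 2^(−7/h) + 2^(−14/h)
- C4D1 EOI = 1 + the sum of 2^(−(84 − s)/h) over the nine earlier doses, given s = 0, 7, 14, 28, 35, 42, 56, 63 and 70 days after the first
- C4D15 EOI = the sum of 2^(−(98 − s)/h) over all twelve doses, adding s = 84, 91 and 98

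Example at h = 12: C1D15 EOI = 1 + 0.667 + 0.445 = 2.11, so C1D1 / C1D15 = 1 / 2.11 = 0.47.

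| Half-life (d) | C1D15 EOI | C1D1 / C1D15 | C4D1 EOI | C4D15 EOI | C4D1 / C4D15 |
|---|---|---|---|---|---|
| 1 | 1.01 | 0.99 | 1.00 | 1.01 | 0.99 |
| 3.5 | 1.31 | 0.76 | 1.08 | 1.32 | 0.82 |
| 6 | 1.64 | 0.61 | 1.34 | 1.71 | 0.78 |
| 12 | 2.11 | 0.47 | 2.17 | 2.63 | 0.82 |

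Over half-lives of 0.5 to 15 days, the Cycle 4 ratio stays between 0.78 and 1.00.

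**3. Could the Q3W data cover the weekly peak?** Suppose the weekly dose is one third of the Q3W dose, the fallback start in Protocol Section 3.1.1 when concentration data are unavailable. The Q3W C1D1 EOI is then 3.00 units, above the weekly C4D15 peak for half-lives up to 12 days (2.63). At 15 days the weekly peak is 3.08, but the Q3W C4D1 EOI is 4.73.

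Part 1A also treated 10 subjects at 1.6 mg/kg (Section 1.5.2). Dividing 1.6 by the C4D15 peaks, their C1D1 EOI exceeds the weekly peak for weekly doses up to 1.6 / 1.32 = 1.21, 1.6 / 1.71 = 0.94 and 1.6 / 2.63 = 0.61 mg/kg at half-lives of 3.5, 6 and 12 days. Coverage is therefore plausible, but depends on how far Part 1B escalates. Section 3.1.1 allows increments of up to 100% until a toxicity trigger.

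**The case against.** The strongest reply is that little is lost. Part 1A subjects have PK-matched triplicates at EOI, at doses up to one judged above the MTD, so a pooled concentration-QTcF model may span the weekly peak. By Cycle 4 the shortfall is at most about 22%. At a 12-day half-life the listed C4D1 EOI triplicate (2.17) already exceeds the Cycle 1 Day 15 peak (2.11). No half-life or Tmax is given for either QT analyte, and for one cleared within a day the gap is negligible. The SAP's maximum post-dose QTcF is not restricted to triplicates, so a post-dose Day 15 ECG would count. The tables also put ECG before PK when both fall at one time point, and infusion times are recorded, so some pairing may be possible.

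Most of this stands, and it limits the size of the problem. It also rules out three things a reader might infer:

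- **That the Day 15 ECG is a single tracing.** No document says so; its replicate number is unstated.
- **That the QT effect at the weekly peak must be extrapolated.** Part 1A may cover the range.
- **That a QW-versus-Q3W contrast is biased toward no effect.** No such contrast is planned. Missing the top of the concentration range widens uncertainty but does not by itself bias a slope.

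The reply does not remove the inconsistency. The Protocol makes the mixed model optional, and no text commits to pooling the regimens. The planned tabulations by dose and study day rely on what is recorded within the weekly regimen. Nothing requires the Day 15 ECG to be taken at EOI.

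**Conclusion.** The point holds as a mismatch between the ECG note, the ECG grid and the PK table for the weekly regimen. Day 15 has a scheduled ECG and scheduled PK samples, but no stated replicate number, timing or pairing. Regimen-specific QTcF data for weekly dosing may therefore miss the highest exposure, mainly in subjects who leave before Cycle 4.

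The listed Day 1 EOI triplicate falls short of the expected peak by about 1%, 24%, 39% and 53% in Cycle 1 at half-lives of 1, 3.5, 6 and 12 days, and by 0% to 22% in Cycle 4. These figures rest on linear kinetics, equal doses, a peak at end of infusion and assumed half-lives. That Day 15 EOI is the peak is itself an inference from those assumptions; it is least secure for unconjugated tubulysin.

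About 24 Part 1B subjects are affected, plus any weekly-schedule Part 2 subjects in the ECG subset. This concerns a secondary objective and does not show that the QT assessment fails. It is worth correcting because the remedy is cheap and the missing pairs cannot be recovered later.

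**What to change.** In the ECG note of Table 5.1-4, which Table 5.1-5 uses by reference, add Day 15 pre-dose and EOI in Cycles 1 and 4 to the PK-matched triplicate list. Pair them with the Day 15 samples already in Table 5.5.1-2. Relabel the Day 8 time point as pre-dose so that it agrees with the weekly PK table. State in SAP Section 7.6.8 that the Day 15 pairs enter the concentration-QTcF analysis.

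The cost is a revised table note, one sentence in the SAP and a few extra tracings at visits where an ECG and PK draws are already scheduled. No new visit or PK sample is needed.

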**Table 5.1-6: Screening and Cycle 1 (Part 3: Nivolumab Combination Arm / 21 Day Cycle) Procedural Outline (CA008002)**

Procedure a	Pre-Screening	Screening Visit D-28 to D-1	C1D1	C1D2	C1D4 b	C1D8	C1D15	Notes
Eligibility Assessments								
Informed Consent		X						A subject is considered enrolled only when a protocol specific informed consent is signed. In Part 3B, if allowed by institutional practices, sites are encouraged to use a pre-screening consent for the mesothelin-expressing tumor analysis. Other screening procedures should not be done before the mesothelin-expressing tumor analysis is available for the determination of subject eligibility.
Inclusion/Exclusion Criteria		X						
ECOG		X	X					
Medical History		X						Also include any toxicities or allergy related to previous treatments. Smoking history for all subjects.
Prior Treatments		X						Including prior cancer treatment regimens and medications administered within 4 weeks of dosing.
Safety Assessments								
PE		X	X					If the screening PE is performed within 24 hours prior to dosing on Day 1 then a single exam may count as both the screening and pre-dose evaluation.

**Table 5.1-6: Screening and Cycle 1 (Part 3: Nivolumab Combination Arm / 21 Day Cycle) Procedural Outline (CA008002)**

Procedure a	Pre-Screening	Screening Visit D-28 to D-1	C1D1	C1D2	C1D4 b	C1D8	C1D15	Notes
								A neurological exam must be included at the screening or pre-dose at the C1D1 visit.
Targeted PE						X	X	To include signs and symptoms of peripheral neuropathy and ocular toxicity. Any grade ocular toxicity requires ophthalmologist consultation and discussion with medical monitor as appropriate.
Ophthalmological Examination c		X						Performed by ophthalmologist or locally qualified personnel. Any abnormality must be discussed with the medical monitor prior to dosing.
Physical Measurements		X	X					Height (screening only), weight.
Vital Signs d		X	X			X	X	Body temperature, blood pressure and heart rate. Blood pressure and heart rate should be measured after the subject has been resting quietly for at least 5 minutes.
Oxygen Saturation		X						Pulse oximetry collected at rest and as clinically indicated on study.
ECGs		X	X	X		X		ECGs should be recorded after the subject has been supine for at least 5 minutes.
MUGA/Echocardiogram		X						MUGA or echocardiogram done at screening to document LVEF.
Laboratory Tests		X	X	X	X	X	X	If the screening laboratory tests are performed within 24 hours prior to dosing on Day 1 then a single exam may count as both the screening and pre-dose evaluation.

**Table 5.1-6: Screening and Cycle 1 (Part 3: Nivolumab Combination Arm / 21 Day Cycle) Procedural Outline (CA008002)**

Procedure a	Pre-Screening	Screening Visit D-28 to D-1	C1D1	C1D2	C1D4 b	C1D8	C1D15	Notes
								Hep B surface antigen and Hep C antibody (if Hep C antibody is positive reflex to Hep C RNA) or Hep C RNA will be done at screening. Note: Testing for HIV-1 and HIV-2 must be performed at sites where mandated by local requirements. See Section 5.3.1 Urine - screening only, unless clinically indicated. C1D4: CBC only.
Thyroid Function		X						TSH with reflexive fT3 and fT4.
Troponin T or I		X	X			X	X	During Part 3A only. The same evaluation must be collected throughout the study.
Pregnancy Test		X	X					
PK and Immunogenicity Assessments (See Section 5.5)								
Biomarker Assessments [REDACTED]								
[REDACTED]								
Tumor Sample (or Archival) Part 3B: Required for Eligibility	X Part 3B only	X (Part 3A and if not pre-screened in						For Part 3B, subjects must have tumor mesothelin expression [REDACTED]. No other protocol-specific eligibility procedures/assessment should be conducted

**Table 5.1-6: Screening and Cycle 1 (Part 3: Nivolumab Combination Arm / 21 Day Cycle) Procedural Outline (CA008002)**

Procedure a	Pre-Screening	Screening Visit D-28 to D-1	C1D1	C1D2	C1D4 b	C1D8	C1D15	Notes
		Part 3B)						until the tumor mesothelin expression is confirmed. Tumor material from archived samples will be used for the IHC analyses. If archived tumor material is unavailable or unsuitable for evaluation, then tumor material from a fresh biopsy must be provided for these analyses. If archived tumor material is to be used, then a tumor paraffin block or unstained slides from a tumor tissue block must be provided. [REDACTED] [REDACTED] Every effort should be made to provide 20 slides (minimum of 10 slides) for mesothelin IHC testing.
Mandatory Fresh Tumor Biopsy Part 3B Only		X						For 10 ovarian cancer subjects and 10 gastric cancer subjects who consent to provide pre- and on-treatment biopsies (C2D1 ±3 days).
Optional Fresh Tumor Biopsy Part 3B Only								For subjects with indications other than ovarian and gastric cancer who consent to provide pre- and on-treatment biopsies (C2D1±3 days).
Tumor Assessment		X						Baseline must be within approximately 30 days of C1D1.

